10.6. Clinical Parameters

Bleeding on Probing (BoP)	(Mühlemann & Son, 1971)
Probing Pocket Depth (PPD)	(Ramfjord, 1967)
Clinical Attachment Level (CAL)	(Ramfjord, 1967)
Plaque Index (PI)	(Löe, 1967)
Gingival Index (GI)	(Löe, 1967)

List of parameters that will be recorded.

1. Bleeding on Probing (BoP); bleeding on probing will be recorded using Sulcus Bleeding Index (SBI) introduced by (Mühlemann & Son, 1971).

Score	Criteria
0	gingiva of normal texture and colour, no bleeding.
1	gingiva apparently normal, bleeding on probing.
2	bleeding on probing, change in colour, no oedema.
3	bleeding on probing, change in colour, slight oedema.
4	either: (a) bleeding on probing, change in colour, obvious oedema; or (b) bleeding on probing, obvious oedema.
5	bleeding on probing and spontaneous bleeding, change in colour, marked oedema.

Graduated University of North Carolina (UNC-15) probe will be used to probe the pocket up until the bottom on four sites of tooth surfaces (the labial, lingual, mesial and distal sites). Then, the bleeding on probing score will be recorded separately on

each four sites according to sulcus bleeding index score as above. Bleeding on probing score of the individual tooth gain by adding all the bleeding score on four sites, divided by four and the bleeding score for an individual gain by adding all the individual tooth score, divided by total numbers of teeth present.

2. Probing Pocket Depth (PPD); the measurement from the gingival margin to the bottom of the pocket will be measured using graduated University of North Carolina (UNC-15) probe to the nearest mm on all six sites of each tooth (mesio-buccal, mid-buccal, disto-buccal, mesio-lingual, mid-lingual and disto-lingual) (Ramfjord, 1967).
3. Clinical Attachment Level (CAL); the measurement from the cemento-enamel junction (CEJ) to the base of the pocket will be measured using graduated University of North Carolina (UNC-15) probe to the nearest mm on all six sites of each tooth (mesio-buccal, mid-buccal, disto-buccal, mesio-lingual, mid-lingual and disto-lingual). If the gingival margin located above the CEJ level, then CAL will be gain by subtracting the probing pocket depth with the distance of gingival margin to the CEJ. If the gingival margin located below the CEJ, then the CAL measurement gain by adding the probing pocket depth with the gingival recession measured (Ramfjord, 1967).

4. Plaque Index (PI); plaque index will be recorded using Silness and Loe, 1967 index.

Score	Criteria
0	No plaque in the gingival area.
1	A film of plaque adhering to the free gingival margin and adjacent area of the tooth. The plaque may only be recognized by running a probe across the tooth surface.
2	Moderate accumulation of soft deposits within the gingival pocket, on the gingival margin and/ or adjacent tooth surface, which can be seen by the naked eye.
3	Abundance of soft matter within the gingival pocket and/ or on the gingival margin and adjacent tooth surface.

Four surfaces of each tooth will be evaluated (buccal/ labial, mesial, distal and lingual/ palatal) and given the score accordingly. To get the score for each tooth, all score from the four area will be added and divided by four. Finally, to get the individual plaque index, all the tooth score will be added and divided by the number of teeth present (Löe, 1967).

5. Gingival Index (GI); Gingival index will be recorded using Loe and Silness 1967 index (Löe, 1967).

Score	Criteria
0	Normal gingiva.
1	Mild inflammation — slight change in color, slight oedema. No bleeding on probing.

2	Moderate inflammation — redness, oedema and glazing. Bleeding on probing.
3	Severe inflammation — marked redness and oedema. Ulceration. Tendency to spontaneous bleeding.

To assess gingival index score, the qualitative changes of the gingiva soft tissue will be examined by direct vision and gentle probing using UNC-15 probe up until the gingival crevice only. Each tooth will be evaluated at 4 sites; buccal/ labial, mesial, distal and lingual/ palatal, and will be given the score according to the criteria listed. To get the score for individual tooth, all the score at the four sites will be added and divided by four. Meanwhile, for individual score, all gingival index score for each tooth will be added and divided by the total number of teeth present.

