10.4. Study Design

This is a single blinded, prospective, randomised split-mouth clinical trial, where quadrants will be divided randomly into control and test groups.

Baseline records of periodontal clinical parameters will be taken for all subjects which include; bleeding on probing index (BoP), probing pocket depth (PPD), clinical

attachment level (CAL), plaque index (PI) and gingival index (GI). All the clinical records will be kept in locked case and delivered after the end of the clinical trial. University of North Carolina (UNC-15) probe will be used to measure the periodontal pocket depth and CAL.

All patients, after the baseline parameters recorded, will then receive motivation and oral hygiene instructions on standard effective oral hygiene practice which include tooth brushing, flossing, interdental brush usage and single tufted brush, followed by full mouth root surface debridement (RSD) under local anaesthesia on all teeth with pocket of ≥ 5 mm (Heitz-Mayfield, 2005; Matesanz-Pérez et al., 2013) using ultrasonic scaler and Gracey's curette, until the root surface feels smooth and clean to an explorer tip of UNC-15 probe (Kaner et al., 2007). For each patient, complete full mouth professional mechanical plaque removal (PMPR) and RSD will be done within 24 hours. All these will be done by main examiner, [name].

Both right (quadrant 1 and 4) and left (quadrant 2 and 3) halves will be assigned randomly to one of the two treatment modalities. A simple randomisation method will be employed to assign 14 participants into two groups (Group 1 and Group 2 corresponding to right halves: test and left halves: control or right halves: control and left halves: test) alternatively. A series of fourteen unique random numbers will be generated using the Numbers RAND() formula, one for each. Patients will then be alternately assigned to Group 1 and Group 2, starting with Group 1, done by supervisor, [name]. The treatment allocation cards will be sealed in envelopes until the clinical procedure.

The subgingival applications of either control (sterilised distilled water) or test (*Lactobacillus reuteri* probiotic) drops will be done based on the randomisation sequences done by [name] before. The allocated group for every subject will only be told to [name] on the

[figure not shown]

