10.7. Group Allocations

Both right (quadrant 1 and 4) and left (quadrant 2 and 3) halves of all 14 participants, split mouth design will be assigned randomly to one of two treatment modalities via computer generated random sequence done by supervisor. A simple randomisation method will be employed to assign 14 participants into two groups (Group 1 and Group 2 corresponding to right halves: test and left halves: control or right halves: control and left halves: test) alternatively. A series of random numbers will be generated using the Numbers RAND() formula, done by supervisor, [name]. The RAND() function in Numbers produces uniformly distributed random numbers between 0 and 1. Fourteen unique random numbers will be generated, one for each participant in the study. The assigned random numbers will be sorted in ascending order from smallest to largest. This

step ensured that the patients will be arranged in a random sequence. Patients will then be assigned to two groups (Group 1 and Group 2) alternatively, starting with Group 1. This process will start with Group 1 and continue with Group 2, then back to Group 1, and so forth, until all patients were assigned to a specific group. The treatment allocation cards were sealed in envelopes until the clinical procedure.

The random allocations sequences will be concealed in a sequential sealed opaque envelope by [name] and will only be opened on the day of intervention's applications. Subgingival applications of either control drops and *Lactobacillus reuteri* probiotic drops will be done by [name].

Groups	Treatment
Control Halves	
On day 0, baseline record will be taken. Then, subjects will receive motivation and oral hygiene instructions on standard effective oral hygiene practice which include tooth brushing, flossing, interdental brush usage and single tufted brush, followed by professional mechanical plaque removal (PMPR) and root surface debridement (RSD). Following this, the control quadrants will be receiving application of the control drops (sterile distilled water) immediately after RSD together with post-operative instructions. Oral hygiene kit will also be given. ([name])
 
Reapplications of control drops together with oral hygiene review visit will be done on day 7, 14, 21 and 28 days after the first subgingival control applications. ([name])
 
Follow up visit for assessment of BoP, PPD, CAL, PI and GI will be done at 3 months interval from the baseline. ([name])

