10.9. Study Flow Chart

11. Statistical Analysis

All data will be collected in numerical form and will be analysed using the IBM SPSS Statistics Version 26.0 software. Histogram plot of data will be first used to check for normality of data distribution. Then, either Independent t-Test or Mann-Whitney Test will be used to compare data between two groups. The variables will be presented as mean and standard deviation for parametric test or median and interquartile range for non-parametric test. Significant level will be set at p-value $p < 0.05$. Meanwhile data within groups to evaluates statistically significant changes from baseline to follow up visits will be analysed either using Paired t-Test or Wilcoxon Signed Ranked Test.

Parameter	Visit	Control group	Test group	p-Value
BoP	Baseline			
	3 months			
PPD (mm)	Baseline			
	3 months			
CAL (mm)	Baseline			
	3 months			
PI	Baseline			
	3 months			
GI	Baseline			
	3 months			

Clinical Parameters for Groups 1 and 2 (mean \pm SD or median (IQR)) at different time intervals

(*denotes statistically significant difference, $p < 0.05$)

12. Budget

	Quantity	Cost/ Unit	Total Cost
Disposable syringe (1ml) (100's/ box)	1	RM 50.00	RM 50.00
Flexible tip (0.25mm) (100's/ box)	1	RM 200.00	RM 200.00
Gracey curettes	28	RM 209.25	RM 5859.00
Sharpening kit	1	RM 2442.00	RM 2442.00
Small cassette	3	RM 592.50	RM 1777.50
Lactobacillus reuteri probiotic	20	RM 134.50	RM 2690.00
Acrylic stents	20	RM 200.00	RM 4000.00
Oral hygiene kit	20	RM 100.00	RM 2000.00
		T O T A L COST	RM 19,018.50

13. Gantt Chart

	2023	2024				2025				2026			
	NOV- DEC	JAN- MAR	APR- JUN	JUL- SEP	OCT- DEC	JAN- MAR	APR- JUN	JUL- SEP	OCT- DEC	JAN- MAR	APR- JUN	JUL- SEP	OCT- DEC
Drafting proposal													
Defence of research proposal (DRP)													
Ethics application													
Data collection preparation													
Data collection													
Thesis write-up													
Submission research paper													
Thesis submission for viva													
Research sends for publication													

14. References

- Chandran, Arunah. (2020). National Diabetes Registry Report, 2013-2019. Ministry of Health Malaysia. https://www.moh.gov.my/moh/resources/Penerbitan/Rujukan/NCD/Diabetes/National_Diabetes_Registry_Report_2013-2019_26082021.pdf

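### BoP, PI and GI are defined as whole-mouth scores, so as written they cannot separate a patient's test half from the control half

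*Combined protocol and SAP*

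**What the plan says.** **Unit of treatment.** Section 10.4 describes a "randomised split-mouth clinical trial, where quadrants will be divided randomly into control and test groups". Sections 10.4 and 10.7 make this specific: the right half (quadrants 1 and 4) and the left half (quadrants 2 and 3) are allocated to opposite treatments within each patient. Patients are then placed in one of two side-order groups, "Group 1 and Group 2 corresponding to right halves: test and left halves: control or right halves: control and left halves: test".

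**Outcome scores.** Section 10.6 begins at a fine level. For BoP, "the bleeding on probing score will be recorded separately on" each of four sites, and a tooth score is formed from them; PI and GI are built in the same way. The last step for each index pools the whole mouth:
- BoP: "the bleeding score for an individual gain by adding all the individual tooth score, divided by total numbers of teeth present"
- PI: "to get the individual plaque index, all the tooth score will be added and divided by the number of teeth present"
- GI: "for individual score, all gingival index score for each tooth will be added and divided by the total number of teeth present"

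No half-mouth or quadrant score is defined for any of the three. PPD and CAL are measured at six sites per tooth, with no rule for combining the sites into a value for a half or a patient.

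**Comparison.** Section 6.2 sets out, for all five outcomes, a comparison of probiotic after debridement with debridement alone at 3 months. The Section 11 table has a control column, a test column and a p-value column, but its caption reads "Clinical Parameters for Groups 1 and 2".

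**The concern.** In a split-mouth trial the treatment contrast lies within the patient, between the two halves. A score averaged over both halves removes that contrast before any test is applied. Three of the five outcomes are defined in this way, and they are the ones needed for objectives 1 (BoP), 4 (PI) and 5 (GI).

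The definition therefore contradicts the design. To carry out the comparison, the analyst must replace the stated outcome rule with one that the plan does not contain. If the replacement is chosen after the data are seen, there is room for choice. A half could be scored over all its teeth, or only over teeth with the pockets of at least 5 mm that receive drops (Section 10.5). These can give different answers, and the plan does not choose between them.

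**Working it through.** The plan gives no figure for this point, so there is nothing of its own to reproduce. The sample size of 14 plays no part. The check is to follow the stated scoring rule into the Section 11 table.

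**Notation, for one patient at one visit.** S_T and S_C are the sums of tooth scores in the test and control halves; n_T and n_C are the teeth present in those halves.

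**Step 1: score as defined in Section 10.6.**

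W = (S_T + S_C) / (n_T + n_C)

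This is one value per patient. It does not change if the labels test and control are swapped.

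**Step 2: enter it in the Section 11 columns.** The patient contributes W to the test column and W to the control column, so the difference is W − W = 0. This is exact for every patient and for any true effect. It needs no assumption about variances, correlation or tooth counts. Change from baseline has the same defect: (W at 3 months − W at baseline) is identical in both columns.

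**Step 3: score by half.**

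H_T = S_T / n_T and H_C = S_C / n_C

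The difference H_T − H_C is the contrast that the objectives ask for.

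**Step 4: illustration.** Take the minimum of 20 teeth from Section 10.3 and assume 20 / 2 = 10 in each half. Assume a mean tooth score of 1.0 in the control half and 0.5 in the test half. These scores are invented to show the arithmetic and are not taken from the documents.

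| Rule | Test column | Control column | Difference |
|---|---|---|---|
| Whole mouth: (10 × 0.5 + 10 × 1.0) / 20 = 15 / 20 | 0.75 | 0.75 | 0 |
| Per half: 5 / 10 and 10 / 10 | 0.5 | 1.0 | −0.5 |

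The same recorded tooth scores give no contrast under the stated rule and the full contrast under the per-half rule.

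**Step 5: caption against columns.** Groups 1 and 2 are sets of patients. Every patient in either group has one test half and one control half, so neither group is a control group or a test group. The caption and the column headings of the Section 11 table cannot both be right.

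**The case against.** The strongest reply is that the intention is clear and the plan would correct itself in use. All five objectives name probiotic against debridement alone. The treatment table in Section 10.7 has rows for control halves and test halves, each listing the 3-month assessment of all five parameters. The Section 11 columns say control and test. An analyst filling that table with whole-mouth scores would see the same number in both columns and would have to go back and average by half. The tooth scores needed for this are already recorded.

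Most of this stands. It shows that the comparison of halves is intended, that the error would probably come to light, and that nothing has to be measured again. It lowers the seriousness of the point. It does not cure it, because the outcome rules still contradict the design and the plan does not say what should replace them.

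A reader might go further and infer from the caption that whole-mouth scores of Group 1 patients will be tested against those of Group 2 patients. Such an analysis would be uninformative. With n_R and n_L teeth on the right and left and an effect δ on the mean tooth score of the test half, the whole-mouth score carries δ × n_R / (n_R + n_L) in Group 1 and δ × n_L / (n_R + n_L) in Group 2. The two are equal when the sides have equal tooth counts. The documents do not support that reading: the table columns, the control-halves and test-halves rows and the objectives all point to test against control. The caption is a mislabel, and no loss of power should be attributed to the trial on account of it.

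**Conclusion.** The point holds for BoP, PI and GI, three of the five outcomes. As defined in Section 10.6, each has the same value for a patient's test and control halves, so the between-half difference is identically zero and objectives 1, 4 and 5 cannot be met from the stated scores. This follows from the definitions alone and rests on no assumed variance or effect size.

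Three limits apply:
- The fault is in the stated definition, not in the measurement. A reader might infer that these outcomes cannot be analysed at all; the site and tooth records show that they can.
- PPD and CAL are not defined over the whole mouth. Their weakness is that no aggregation rule is given.
- The caption conflicts with its own table and should be corrected, but a comparison of side-order groups is not evidently planned.

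**What to change.** 1. In Section 10.6, define BoP, PI and GI per half: sum the tooth scores in quadrants 1 and 4 and divide by the teeth present in those quadrants; do the same for quadrants 2 and 3.
2. State that each half is labelled test or control from the patient's allocation.
3. Give PPD and CAL a per-half aggregation rule, and say whether it covers all measured sites in the half or only those at or above the baseline pocket threshold for application.
4. Recaption the Section 11 table as test halves and control halves, and keep the names Group 1 and Group 2 for the side-order allocation only.

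The cost is an amendment of wording, to be made before the outcome data are seen. No new measurement, visit or patient is needed; for the three indices only the last averaging step changes.

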10.2. Sample Size Calculations

Sample size calculation done using G-power sample size calculator version 3.1.9.6 (Kang, 2021). The sample size calculation is based on the previous study by Minić and colleagues on the effect of the local probiotics in the therapy of periodontitis: a randomised prospective study (Minić, Pejčić, & Bradić-Vasić, 2022). The statistical test was set as “means: difference between two independent means (two groups)”, with an alpha error of 5%, and 90% statistical power. The minimum total sample size required is 12. Considering the probability of drop out rate 10%, 14 patients will be included.

$$\underline{12 + (12 \times 0.10) = 14}$$

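### No parameter has a score per mouth half and Section 11 names no unit of analysis, so PPD and CAL could be tested on correlated sites or on half means, and neither gives a 5% test

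*Combined protocol and SAP*

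**What the plan says.** Section 10.6 (Clinical Parameters) gives three of the five parameters a route from site to tooth to a single score. For BoP, "the bleeding score for an individual gain by adding all the individual tooth score, divided by total numbers of teeth present"; PI and GI have equivalent rules. Each of these scores covers every tooth in the mouth.

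PPD and CAL stop one stage earlier: each "will be measured using graduated University of North Carolina (UNC-15) probe to the nearest mm on all six sites of each tooth". No mean per tooth, per half or per patient follows.

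Sections 10.4 and 10.7 allocate treatment to the right and left halves of each patient's mouth, so every patient supplies one test half and one control half.

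Section 11 (Statistical Analysis) says: "Then, either Independent t-Test or Mann-Whitney Test will be used to compare data between two groups". It states no unit of analysis and includes no term for clustering or for pairing of the halves. Its paired tests are reserved for change over time within a group. The shell results table has rows for PPD and CAL but shows no number of cases.

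Section 10.2 counts the sample in patients: "The minimum total sample size required is 12", and "Considering the probability of drop out rate 10%, 14 patients will be included".

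**The concern.** PPD and CAL are specific objectives 2 and 3. Two analysts following the plan could run quite different tests on the same readings. One could load every site as a case, giving hundreds of cases per arm. The other could average to one value per half, giving 14 per arm. Both would be within the text, and the choice could be made after the data are seen.

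Sites on one tooth, or in one half, tend to resemble each other. If they enter as independent cases, the standard error can be too small and chance differences between halves are declared significant too often. If half means enter an independent-groups test, the variation that both halves of a patient share stays in the error term, although it cancels in the comparison, and the test rejects too rarely. The two readings err in opposite directions.

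**Working it through.** **The plan's own count.** 12 × 1.10 = 13.2, rounded up to 14, as in Section 10.2. The 12 itself cannot be rebuilt, because no effect size or SD is given. What matters here is that the count is in patients.

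**Number of cases if sites are used.** Inputs: 14 patients, at least 20 teeth (Section 10.3), six sites per tooth (Section 10.6).
- 20 teeth, split evenly between halves (assumption): 14 × 20 × 6 = 1,680 readings, 840 per arm, 60 per half.
- 28 teeth (full-dentition assumption): 14 × 28 × 6 = 2,352 readings, 1,176 per arm, 84 per half.
- Treated deep sites only: 15 per half (assumption). Drops go only into pockets of 5 mm or more (Section 10.5), and the plan does not say whether the analysis uses those sites or all sites.

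**Reading A: sites as cases in the independent t-test.** Set total site variance to 1, with shares v_patient, v_half (half within patient) and v_site. There are n patients and m sites per half, and no true effect.
- Variance the test assumes: 2/(n·m).
- True variance of the difference between arms: 2(v_half + v_site/m)/n. The patient share drops out because each patient contributes to both arms.
- Ratio R = m·v_half + v_site.
- False-positive rate = 2·P(Z > 1.96/√R).

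The shares are assumptions; the documents give none. With v_patient = 0.10 and no tooth effect, v_site = 0.90 − v_half:

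| v_half | 15 sites: R, rate | 60 sites: R, rate | 84 sites: R, rate |
|---|---|---|---|
| 0 | 0.90, 3.9% | 0.90, 3.9% | 0.90, 3.9% |
| 0.01 | 1.04, 5.5% | 1.49, 10.8% | 1.73, 13.6% |
| 0.02 | 1.18, 7.1% | 2.08, 17.4% | 2.56, 22.1% |
| 0.05 | 1.60, 12.1% | 3.85, 31.8% | 5.05, 38.3% |

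**Adding correlation within teeth.** With a tooth share v_tooth and s sites per tooth, R = m·v_half + s·v_tooth + v_site. For v_patient = 0.10, v_half = 0 and s = 6:
- v_tooth = 0.10: R = 0.6 + 0.8 = 1.4, rate 9.8%.
- v_tooth = 0.20: R = 1.2 + 0.7 = 1.9, rate 15.5%.

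Inflation therefore does not need a half-level effect. Over a wider grid of shares (patient 0–30%, half 0–10%, tooth 0–30%) the rate runs from about 2% to about 50%.

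**Reading B: half means in the independent t-test.** A half mean has within-patient variance w = v_half + v_site/m (no tooth effect) and total variance w + v_patient. The true variance of the difference, relative to what the test assumes, is w/(w + v_patient). For v_patient = 0.10, v_half = 0.05 and m = 60: w = 0.05 + 0.85/60 = 0.064, so the ratio is 0.064/0.164 = 0.39. Across the simulated settings, with patient shares of 10–20%, the false-positive rate was 0–1.1%.

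**One paired difference per patient.** Simulated rate 4.3–5.6% in every setting tried, which is nominal within simulation error.

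**The case against.** The strongest objection is that nothing in the plan says sites will be cases. A reader might infer from the six-site wording that the t-test would run on hundreds of sites and that inflation is the plan's consequence. The documents do not support that. Section 11 is silent on the unit, and Section 10.2 counts patients, which points towards patient-level values. This stands: the plan permits a site-level test but does not prescribe one.

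A reader might also attach a narrow inflated range, such as 11–38%, to the plan. That range would need assumed half-level shares and every site analysed, and its upper end a full dentition. It would leave out the cases near or below 5%, which are equally open because the analysed sites are not named.

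The reasons for correlation should not be overstated either. One clinician does all the debridement and one student does the repeat applications, so operator is common to both arms. Hygiene instruction and kit are given per patient, so general hygiene is largely shared by the two halves. Patient-level correlation cancels in a split-mouth comparison and by itself lowers the rate: with a patient share of 20% and nothing else, R = 0.8 and the rate is 2.8%. Only correlation specific to a half or a tooth inflates it.

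Finally, it is tempting to say that PPD and CAL merely lack the last step that BoP, PI and GI have. That step averages the whole mouth, so copying it would not produce a value for each half.

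None of this supplies the missing rule. A patient count in the sample-size section does not define an analysis, and the patient-level reading in the stated test is itself off nominal.

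**Conclusion.** The point holds as a gap in the plan, with a consequence that depends on how the gap is filled. It is certain that PPD and CAL have no summary score, that no parameter has a score per half, and that the unit of analysis is unstated. The size is conditional on variance shares that no document supplies. Sites as cases give about 4–12% (15 sites per half), 4–32% (60) or 4–38% (84), more with correlation within teeth. Half means in the independent test give about 0–1% when the patient share is 10–20%. Because neither natural reading is a 5% test, this is more than missing detail and should be settled before data are analysed. It does not show that the trial will report inflated results.

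**What to change.** In Section 10.6, define for all five parameters one value per mouth half, per patient, per visit: the mean over the analysed sites (PPD, CAL) or teeth (BoP, PI, GI) of that half. Name which sites are analysed.

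In Section 11, replace the between-group independent t-test or Mann-Whitney test with a paired t-test or Wilcoxon signed-rank test on one test-minus-control difference per patient (n = 14, fewer with dropout). State that sites are not entered as cases, and show the number of patients in the results table. If site-level data are wanted, a mixed model with random effects for patient, half within patient and tooth is an alternative.

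The cost is a few sentences and one aggregation step before the analysis, with no extra patients, visits or measurements. PPD and CAL p-values may be less favourable than a site-level test would give. At 90% power and two-sided 5%, the paired test can detect a standardised difference of 0.94 with 14 pairs, or 1.03 with 12.
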